Usual care + incentives. Participants in this condition will receive the usual-care services from their providers described above plus a 12-week program of monetary incentives for verified smoking abstinence (maximum earnings = \$810 over 12 wks) that will be implemented by our clinic staff. The initial smoking negative test (< 6 ppm) will be worth \$10. Each consecutive negative test increases the incentive by \$2.50, with the 2nd consecutive negative test worth \$12.50, the 3rd negative test \$15, the 4th test \$17.50, etc. Incentive value continues to escalate upward based on consecutive negative test results with a maximum value of \$50. A positive test or failure to submit a specimen for a scheduled test resets incentive value back to the initial \$10. This reset contingency protects against relapse once a period of abstinence has been achieved (Roll & Higgins, 2000). Two consecutive negative tests following a reset will return incentives back to the value that they were at prior to the positive test result. Based on prior studies (Heil et al., 2008), we anticipate mothers will earn about 40% (\$324) of the maximum possible. Use of NRT or other

pharmacotherapies in this condition will not be prohibited in keeping with usual care being a component of this condition, but study staff will not offer them the pharmacotherapy protocol described below. Based on our prior studies with incentives for smoking cessation and those of others in disadvantaged populations, we are confident that there will be minimal ongoing pharmacotherapy use in this condition or the usual care condition above (<10%) (Coleman et al., 2012; Heil et al., 2008; Hiscock et al., 2012; Yoon et al., 2009). Economically disadvantaged smokers under-utilize smoking-cessation pharmacotherapies (e.g., Coleman et al., 2012; Hiscock et al., 2012).

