Usual care + incentives + pharmacotherapy. Mothers in this condition will receive the counseling and incentives protocols described above and the following pharmacotherapy protocol: (1) A clear recommendation will be provided by our clinic staff to use NRT. For those who agree, we will immediately register them with the Vermont Quit Network if they have not already done so asking for a supply of free NRT as part of the registration and using our clinic address as the delivery site. We will have NRT already available onsite that we will use so that the pharmacotherapy protocol can be implemented immediately after a woman agrees to use it. That supply can be replenished as needed when the requested package arrives from the state. We will use the medications provided through the Vermont Quit Network (over-the-counter NicoDerm CQ, GlaxoSmithKline Consumer Healthcare). (2) Following their quit date, participants will be encouraged to follow a standard 10-wk course of transdermal NRT, using the 21 mg/24 hr patch for 6 more wks, the 14mg/24 hr patch for 2 wks, and the 7 mg/24 hr patch for the final 2 wks. Additionally, participants will be encouraged to use nicotine lozenges (or gum if someone objects to the lozenges) in combination with transdermal NRT beginning on their quit date as a behavioral substitute for smoking. We will use Commit (GlaxoSmithKline Consumer Healthcare) brand of 2 or 4 mg lozenges in various flavors, with those who smoke within 30 min of awaking using the higher dose and those who first smoke later than 30 min using the lower dose as per package insert. We will encourage use of the lozenges for 10 wks. Women will pick up one-week supplies of NRT patch and lozenges at their first clinic visit each week. The project nurse will assess medication side effects at each visit, and recommend adjustments in dose and other aspects of the regimens described above as warranted and in consultation with the clinic medical director.

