
Economic Evaluation, Cost analysis.

We will conduct a cost-effectiveness analysis (CEA) from the societal perspective (Drummond et al., 2005). First, to determine

the cost of each intervention, we will employ the Brief Drug Abuse Treatment Cost Analysis Program (Brief DATCAP; French et al., 2004), which has been widely used in the area of substance abuse (e.g., French et al., 2008; Roebuck et al., 2003; 2009; 2011; <http://datcap.com/>), including incentives projects (Knealing et al., 2008). The economic cost of treatment will be derived by allocating fixed costs based upon the proportion of time or space utilized by the programs and costs that vary by patient engagement and smoking status (e.g., drug tests, financial incentives). The total cost per treatment episode will be individual-specific, and will also include the opportunity cost of the patient's time while in treatment as measured by the Client (Outpatient) version of the DATCAP (French 2005; Salomé et al., 2003). The time period of the cost analysis will span from intake to discontinuation or completion of the program. The cost of all research-specific resources consumed will be excluded from the evaluation. All costs and benefits will be expressed in a common dollar year. Estimated treatment costs will be combined with the estimated child healthcare utilization costs to represent total costs per treatment condition. Cost-effectiveness analysis. CEA will be conducted wherein the average (mean) difference in treatment costs across the three treatment conditions will be divided by the average (mean) difference in each outcome to derive incremental cost-effectiveness ratios (ICERs). Statistical significance of these ICERs will be determined by employing non-parametric bootstrapped standard errors (Drummond et al., 2005). A special form of CEA, cost-utility analysis (CUA), will be performed. Based upon smoking status from the quit date through the 48-week assessment, the number of quality-adjusted life years (QALYs) gained by the mother—as measured by the proportion of time spent in 'smoking' and/or 'non-smoking' status will be derived using QALY weights recommended in the extant literature (e.g., Cromwell et al., 1997; Flack et al., 2007). We will estimate relapse curves beyond the 48-week assessment from the literature to estimate longer-term outcomes. QALYs gained by each child based on changes in their biochemically verified SHSe will be similarly calculated using QALY weights recommended in the literature (Taylor, 2009). The incremental cost per QALY gained between the three treatment conditions will be calculated and compared for mothers and children separately and also summed across mothers and children. In conducting analyses for children, we will assume that all children residing fulltime with the mother share the same smoking status as the target child.

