
Risks/Benefits: Describe any potential or known risks. This includes physical, psychological, social, legal or other risks. Estimate the probability that given risk may occur, its severity and potential reversibility. If the study involves a placebo or washout period, the risks related to these must be addressed in both the protocol and consent. Describe the planned procedures for protecting against or minimizing potential risks and assess their likely effectiveness. Where appropriate, discuss plans for ensuring necessary medical or professional intervention in the event of adverse effects to the subjects. Discuss the potential benefits of the research to the subjects and others. Discuss why the risks to the subjects are reasonable in relation to the anticipated benefits to subjects and others. Discuss the importance of the knowledge gained or to be gained as a result of the proposed research and why the risks are reasonable in relation to the knowledge that reasonably may result. If there are no benefits state so.

Risks:

- The participant may feel uncomfortable answering some of the questions. We will work with them to minimize this discomfort and no one has to answer any question that they do not wish to.
- There is a risk that confidential information might accidentally be disclosed, including illegal drug use results. Professional standards for protecting confidential information (detailed below) will be used to minimize this risk.
- Participants in this study may experience withdrawal. These symptoms can include anger, irritability, frustration, anxiousness, depressed mood, craving for cigarettes, difficulty concentrating, increased appetite, weight gain, sleep problems, restlessness, impatience, constipation, dizziness, coughing, nightmares, nausea, and sore throat. If these mood changes appear to put a participant's health at risk they will be asked to stop participating in the study.
- There is a risk of COVID-19 transmission during curbside pickup of urine samples. Research staff will conduct wellness checks before scheduled visits. If either the participant or the staff person reports any symptoms of COVID-19, curbside pickup of the sample will be postponed until a later date. If no symptoms are reported, staff will use the social distancing protocol detailed above in the Methods and Procedures section to collect the sample while minimizing physical contact with the participant.

Benefits:

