Define criteria to be used for decision making regarding continuation, modification, or termination of the entire study (not individual participation) (i.e. "stopping rules").

In the proposed study, we will use the FDA's definition of Adverse Events (AEs) and Serious Adverse Events (SAEs). AEs and SAEs will be assessed at each subject visit by a trained staff member and copies of all reports noting AEs and SAEs will be kept in a central file as well as in the individual subject's chart. AEs and SAEs will be discussed at the weekly research meetings. There are no predefined "stopping" rules for this study. However, the study may be terminated if the investigators determine that the frequency of AEs and SAEs warrants discontinuation.

Modifications may be made to the study if the PI determines that participants recruitment is not progressing satisfactorily. Specifically, recruitment may be expanded to partners outside of WIC or the UVM Health Network in an effort to meet recruitment goals.

What will be the frequency of the review? Please note that the frequency of reviews should be commensurate with the risk of the study. At a minimum, a review of the data should be conducted annually at time of continuing review. **Forward copies of the data and safety monitoring reports to the 1) IRB, 2) CRC (if applicable), and/or 3) UVMCC (if applicable).**

	Monthly		Annually
	Quarterly		Other (e.g. by dosing level, no. of subjects enrolled):
	Bi-annually		

Will the sponsor be conducting data monitoring visits for this study?

Yes No NA

If yes, how often?

--

Adverse Event, Unanticipated Problem (UAP), Reportable New Information (RNI): Describe how events and UAPs will be evaluated and reported to the IRB. All protocols should specify that, in the absence of more stringent reporting requirements, the guidelines established in the "Adverse Event and Unanticipated Problems Reporting Policy" will be followed. The UVM/UVM Medical Center process for review of adverse events and UAPs to subjects or others should be included in the DSMP.

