Any SAE will be brought to the attention of the PIs and the study physician as soon as possible and not longer than 24 hours. Any AE or SAE that is both unexpected and related to study participation will be reported to the IRB within 7 days of the event. The IRB will make a determination as to whether additional reporting requirements are needed. IRB actions will be reported to the funding agency by the PIs no less than annually and more frequently as recommended by the local IRB. Any SAEs will be summarized in the yearly Progress Reports to the funding agency, including a review of frequency and severity. All SAEs will be followed through ongoing consultation with the physician caring for the patient until they resolve, result in death, or stabilize and are not expected to improve. The study staff will be in close contact with participants and health care providers throughout the study to monitor for potential unanticipated problems. Any unanticipated problems will be discussed at the weekly research staff meetings and reported as required to the CHRMS using the Report of Protocol-Related Problems & Deviations Form.

Withdrawal Procedures: Define the precise criteria for withdrawing subjects from the study. Include a description of study requirements for when a subject withdraws him or herself from the study (if applicable).

There are no predefined criteria for withdrawal from the study. However, participants may be withdrawn if the PI determines it is not advisable that they continue on in the program. Participants may withdraw themselves at any time, for any reason.

Sources of Materials: Identify sources of research material obtained from individually identifiable human subjects in the form of specimens, records or data. Indicate whether the material or data will be obtained specifically for research purposes or whether use will be made of existing specimens, records or data.

Sources of material will include:

- Questionnaires on demographics (age, marital status, education, etc.) and physical and mental health
- Questionnaires about cigarette use, withdrawal and cravings, as well as thoughts and feelings about smoking
- Urine and breath samples that measure recent cigarette use and exposure to tobacco byproducts
- Questionnaires about the time and effort required to attend study-related visits
- Tasks that measure the value of cigarettes and the strength of preference for money available now compared to money available later

DRUG INFORMATION

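### Women stopped for withdrawal-related mood changes are asked to leave the study; nothing provides for stopping only the intervention and keeping the scheduled assessments

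*Protocol*

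**What the plan says.** The Risks list (Protocol, Risks/Benefits) names nicotine-withdrawal symptoms, depressed mood among them, and then gives the rule: "If these mood changes appear to put a participant's health at risk they will be asked to stop participating in the study".

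Other places that bear on it:

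- **Protocol, Withdrawal Procedures.** There are no predefined criteria and women may leave whenever they wish. In addition, "participants may be withdrawn if the PI determines it is not advisable that they continue on in the program". Nothing is said about later assessments.
- **Protocol, Usual care + incentives + pharmacotherapy.** The nearest thing to a smaller step is: "The project nurse will assess medication side effects at each visit, and recommend adjustments in dose and other aspects of the regimens". It covers medication side effects in one arm.
- **Protocol, Follow-up Assessments and Statistical Considerations.** The battery is planned for every mother and child at four time points, and every randomized woman is analysed whatever her dropout or compliance. Neither section addresses women who were asked to stop.
- **SAP, Intention-to-Treat Population and Missing Data.** Missing maternal smoking status counts as smoking. Incomplete child cotinine data are handled by maximum likelihood.
- **Protocol, Data Safety and Monitoring and the adverse-event section.** "AEs and SAEs will be assessed at each subject visit by a trained staff member". Also, "All SAEs will be followed through ongoing consultation with the physician caring for the patient until they resolve, result in death, or stabilize".

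**The concern.** The rule takes the largest available step. A woman whose mood worsens while she tries to quit may need the quit attempt, the incentives or the NRT stopped. That is no reason to stop measuring her or her child. If her assessments end as well, three things follow.

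1. **Safety.** The depression inventory, symptom inventory and withdrawal scale, given at each assessment, and the visit-based adverse-event review all stop. They stop for the very women in whom the named risk became a concern.
2. **Primary aim 1.** Her 12- and 24-week smoking status is assigned instead of observed. Withdrawal symptoms are tied to quitting, so these removals may be related to the outcome.
3. **Primary aim 2.** Her child's urine cotinine is no longer collected, because of the mother's symptoms and not the child's.

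The intention-to-treat rule keeps her in the analysis but does not collect her data.

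**Working it through.** **Step 1: what the wording supports.** The Risks list speaks of *the study*; Withdrawal Procedures speaks of *the program*. Elsewhere the latter word means the intervention: the incentive arm is a "12-week program of monetary incentives for verified smoking abstinence". The economic section already separates the two ideas. For costs, "The time period of the cost analysis will span from intake to discontinuation or completion of the program". For quality-adjusted life years, the basis is different: "Based upon smoking status from the quit date through the 48-week assessment". So the plan relies on follow-up that can outlast the intervention, but the mood rule does not provide for it. Staff could act on the two sections in different ways. The plain reading of the Risks list is that assessments end too, although no sentence says so outright.

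**Step 2: what is lost per woman on that reading.** Assessments fall at weeks 6, 12, 24 and 48, at $35 each (Protocol, Follow-up Assessments).

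| Removed | Assessments left | Primary smoking endpoints lost | Child cotinine results lost | Planned payments |
|---|---|---|---|---|
| before week 6 | 4 | 12 and 24 weeks | 4 | 4 × $35 = $140 |
| weeks 6–12 | 3 | 12 and 24 weeks | 3 | $105 |
| weeks 12–24 | 2 | 24 weeks | 2 | $70 |
| weeks 24–48 | 1 | none | 1 | $35 |

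The abstinence-monitoring visits number 5 + (2 × 7) + 4 = 23. Keeping the assessments restores none of these.

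For scale, the protocol expects 85–90% follow-up compliance. That already leaves 0.10 × 80 = 8 to 0.15 × 80 = 12 women per arm missing, and removals would add to them.

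**Step 3: the plan's power figures.** Inputs are 80 per arm and two-sided alpha 0.05 (Sample Size Justification). With a pooled-variance normal approximation,

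power = Φ{[|p1 − p2|√n − 1.96√(2p̄(1 − p̄))] / √(p1(1 − p1) + p2(1 − p2))}.

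- 40% vs 15%: (0.25 × 8.944 − 1.96 × 0.6315)/0.6062 = 1.647, power 0.950 (stated .95).
- 20% vs 5%: (0.15 × 8.944 − 1.96 × 0.4677)/0.4555 = 0.933, power 0.825. Fisher's exact test gives 0.793 (stated .80).

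**Step 4: illustration only.** The removal shares are assumed, because the documents give none. Let s be the share removed and r their abstinence relative to the planned rate for their arm. The scored rate is p × (1 − s × r). For example, with s = 5% and r = 1, 0.40 × 0.95 = 0.380 and 0.15 × 0.95 = 0.1425.

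| Scenario | s = 2% (1.6 women/arm) | s = 5% (4) | s = 10% (8) |
|---|---|---|---|
| 12 weeks, both arms, r = 1 | 0.945 | 0.935 | 0.917 |
| 12 weeks, both arms, r = 0.5 | 0.947 | 0.943 | 0.935 |
| 12 weeks, incentive arm only, r = 1 | 0.938 | 0.917 | 0.869 |
| 24 weeks, both arms, r = 1 | 0.816 | 0.801 | 0.776 |
| 24 weeks, both arms, r = 0.5 | 0.820 | 0.813 | 0.801 |
| 24 weeks, incentive arm only, r = 1 | 0.809 | 0.783 | 0.736 |

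If none would have been abstinent (r = 0), scoring them as smokers is correct and power is unchanged.

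On direction: at 12 weeks with s = 5% and r = 1 in both arms, 4 × 0.40 = 1.6 abstainers are scored as smokers in the incentive arm and 4 × 0.15 = 0.6 in usual care. That is conservative for incentives versus usual care. For incentives plus NRT versus incentives alone, the documents do not settle the direction.

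**The case against.** The strongest reply is that the Risks list is a bullet in an ethics-committee form and that women are only asked to stop. The sections that govern outcomes lean towards retention: assessments for every mother and child, analysis regardless of dropout, and a withdrawal section that speaks of the program. The consent forms, one for the mother and one for the child, are not in our copy and may allow continued follow-up. This has force against claiming that the plan orders follow-up to end. It does not remove the gap, because none of those sections addresses women who were asked to stop, and the Risks list is the more specific rule.

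It is also fair that much of the safety net remains. Serious events are followed, Crisis Services is called for thoughts of harm, current affective disorder and suicidality are excluded at entry, and child health records are requested through 48 weeks where the mother agrees. So the safety gap is narrow: mood scales and non-serious events.

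Two limits on the remedy stand:

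- In usual care the study has no hand in the counselling content, so there is little study-delivered intervention to stop.
- A reader might infer that the remote COVID procedures would recover the primary endpoint. They would not. The abstinence definition in Statistical Considerations needs self-report, breath CO below 6 ppm and laboratory urine cotinine below 50 ng/ml. The video saliva screen gives a positive or negative result at 30 ng/ml, has no CO reading, and cannot separate NRT from smoking as anabasine and anatabine testing can.

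Finally, the protocol already refers to existing participants in 2020 and the SAP is dated April 2023, so the number of women who could still benefit is unknown.

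**Conclusion.** The point holds as a cheap improvement that should be made. The plan states a rule for at-risk women and provides no way to stop the intervention alone. Followed on its plain reading, the rule replaces up to two observable primary smoking outcomes per woman with an assumed value, leaves up to four child cotinine results to modelling, and ends mood-scale and non-serious adverse-event review.

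The number of women is not given and is probably small. Two stronger inferences are not supported. These women are not dropped from the analysis: they stay in it with assigned or modelled values. Nor is a material loss of power shown: every power change above depends on an assumed removal share and assumed abstinence among those removed. The conclusion rests on ascertainment and safety data, and on the consent forms not already providing for follow-up. If they do, the Risks list should say the same.

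**What to change.** Replace the sentence in the Risks list with wording such as:

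> If mood changes appear to endanger her health, the study clinician may stop the quit attempt, incentives, NRT and/or abstinence-monitoring visits, as they apply to her arm. She and her child will still be invited to the remaining scheduled assessments, with adverse-event review, unless she withdraws consent.

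In Withdrawal Procedures, add that stopping the intervention is not withdrawal from the study. Report by arm the number of women stopped for mood changes.

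Prefer the standard assessment: breath CO plus laboratory urine cotinine, with anabasine/anatabine where NRT is used. The phone survey and curbside child urine are acceptable fallbacks. The video saliva screen should not be described as yielding the primary endpoint. The clinical threshold stays with the sponsor's clinicians. The missing-equals-smoking rule needs no change, since it applies only to missing data.

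Cost: one or two sentences in each of two sections, matching consent wording, and possible re-consent of women already enrolled. There are no new visits. Each assessment takes about an hour plus staff time, and the $35 payments (at most $140 per woman) are already planned. Some women judged to be at risk may not want further contact; they may decline.

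If follow-up is already complete, the part that remains useful is reporting the number stopped by arm.

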Inclusion of Children: Describe efforts to include children. Inclusion is required unless a clear and compelling rationale shows that inclusion is inappropriate with respect to the health of the subjects or that inclusion is inappropriate for the purpose of the study. If children are included, the description of the plan should include a rationale for selecting or excluding a specific age range of children. When included, the plan must also describe the expertise of the investigative team in working with children, the appropriateness of the available facilities to accommodate children, and the inclusion of a sufficient number of children to contribute to a meaningful analysis relative to the purpose of the study. Provide target accrual for this population. Identify whether children are wards of the state. **If children are excluded** then provide appropriate justification.

Children under 12 will be included in this study. As this study aims to measure reduction in child exposure to second-hand-smoke, inclusion of children is crucial. Children 12 and older will not be included as the chances of children using tobacco products themselves increase substantially at that age.

For protocols including the use of an investigational drug, indicate whether women of childbearing potential have been included and, if not, include appropriate justification.

n/a

If HIV testing is included specifically for research purposes explain how the test results will be protected against unauthorized disclosure. Include if the subjects are to be informed of the test results. If yes, include the process and provision for counseling. If no, a rationale for not informing the subjects should be included.

Not applicable

Will the SONA psychology Pool be utilized? Include documentation indicating permission to use this recruiting tool

Yes No

FINANCIAL CONSIDERATIONS

Describe all potential research related expenses to subjects:

There will be no added expense to the participant for participation in this study.

Compensation for participation: Describe all plans to pay subjects, either in cash, a gift or gift certificate. Please note that all payments must be prorated throughout the life of the study. The IRB will not approve a study where there is only a lump sum payment at the end of the study because this can be considered coercive. The amount of payment must be justified. Clarify if subjects will be reimbursed for travel or other expenses.

Not applicable

All subjects will receive \$35 compensation for their time for each of the 5 assessments. Subjects in Treatment A will receive \$15 in financial incentives for each of the 23 study visits. Subjects in Treatments B or C will receive financial incentives for the 23 study visits only if they demonstrate biochemically-verified smoking abstinence. Incentives for these visits start at \$10 and max out at \$50 (details of schedule are described above). Important to clarify is we consider the \$35 for each follow-up assessment as compensation. However, we consider financial incentives for attending sessions and abstaining from smoking as therapeutic interventions (i.e., therapy) and not compensation for study participation.

Collaborating Institutions

Will this research be conducted in collaboration with other sites at other locations?

Yes No X

If so, complete the following for all collaborating institutions:

Institution Name	Describe Involvement	Is there an IRB? If yes, attach approval or explanation	Are other permissions required? If yes, attach approval or explanation

INFORMED CONSENT

a. Type of Consent

i. Are you obtaining Written Consent?

Yes No
 Yes No

If yes, will there be more than one consent document?

If yes, how many consent documents and for what populations.

Two consent forms will be used, one for the mother and one for the child. One HIPAA form will be used for the child.

ii. Are you requesting a Waiver of Informed Consent?

Yes X No

This request means that you will not be obtaining verbal nor written consent. If yes, complete the form Request for a Waiver of Informed Consent/Authorization/Documentation in UVMClick.

iii. Are you requesting an Alteration of Informed Consent Procedures?

Yes X No

This is a request to alter an individual's informed consent or elements of informed consent. Deception in research would be one example when consent would be altered. See [Policies and Procedures Manual](#) for more information about when a subject's consent may be altered. If yes, complete the smart form Request for a Waiver of Informed

Consent/ Authorization/ Documentation in UVMClick.

iv. Are you requesting a Waiver of Documentation of Informed Consent? Yes No
 This request means you are obtaining verbal or implied consent without obtaining the subject's signature on a consent form. See manual for the criteria required to obtain this type of waiver.

If yes, complete the form Request for a Waiver of Informed Consent/Authorization/Documentation in UVMClick.

v. Do you intend to obtain consent from a legally authorized representative? Yes No
 If yes, describe the process.

vi. Are you requesting a short form consent process for non-English speaking subjects? Yes No
 If yes, please describe. Guidance available in the [Policies and Procedures Manual](#).

b. Consent Process

i. Once a prospective subject is identified, who initiates the informed consent discussion and answers questions presented by the subject or the subject's family?
 The PI or an authorized representative will initiate the informed consent discussion and answer questions presented by the subject or subject's family.

ii. Where (in what setting) is the informed consent process initiated? How much time is the subject given to decide?
 Those who are eligible will be invited to the clinic for an in-person session. Those eligible may have as much time as they need to review the informed consent form before deciding to participate.

iii. Is the principal investigator present for the initial and subsequent informed consent discussions with the subject?
 The PI or an authorized representative will be present for the initial and subsequent informed consent discussions with the subject.

iv. What other method of documentation is used to record the informed consent process, in addition to the executed consent form? See an [example of documentation](#) of the informed consent **process** under consent templates on our forms page. (This separate documentation is required to document the consent process with the research subject)
 One HIPAA form will be used to the child.

Information Withheld From Subjects: Will any information about the research purpose and design be withheld from potential or participating subjects? If so, explain and justify the non-disclosure and describe plans for post-study debriefing.

Not applicable

Research Data Management Plan: The Research Data Management and Security Plan form must be completed. The form, along with guidance, can be found in our [forms library](#) and must be submitted with your initial application.
